5.1 Description

This study is **neither a drug nor a device trial**. Patients will be administered FDA approved ICG through intravenous injection and imaged by a FDA approved surgical microscope (Spy Elite) which is 0.5 meter away from the subject. Both ICG fluorescence and the two imaging systems have been used for routine clinical practice for many years. Figure (a) shows the Schematic sketch of the imaging systems. ICG fluorescence imaging utilizes intravenously injected ICG, which is a fluorescent dye that is FDA-approved for clinical use, illuminated with near-infrared light. The ICG dye is indirectly activated and the dynamic fluorescence due to bone perfusion can be captured by a video rate imaging system.

5.2 Preparation and Administration of Study Drug

ICG used in this study is purchased from Novodaq/Stryker.

ICG Preparation and Administration Procedures:

- 1) ICG is prepared by the Surgical and/or Anesthesia teams in the operating room on the day of surgery.
- 2) From the vial containing ICG, the required dose is withdrawn into a syringe, labeled, and administered through a peripheral intravenous line followed by a saline flush.

Prior to ICG administration, patients will undergo standard preoperative monitoring by the Same Day nursing staff that includes continuous pulse oximetry, blood pressure monitoring, and heart rate, and respiratory rate. These results will be available prior to surgery and prior to administration of ICG. ICG will be administered by an anesthetist in the operating room. Patients are under the care and observation of the anesthesia and surgical teams during this time. Postoperatively, patients are transferred to the Post-Anesthesia Care Unit (PACU) where they are monitored continuously by nursing staff supervised by anesthesiologists. During this entire time vital signs (including temperature, pulse, respiratory rate and blood pressure) are collected as standard of care. All clinical data will be reviewed for adverse events for a period of 30 minutes post-injection,

Day of surgery Procedures	Pre-Infusion	0-30 minutes post-infusion
Pulse	X	X
Blood Pressure	X	X
Temperature	X	X
Respiratory Rate	X	X
Adverse Events		X

A Pulse dye densometer (Pulsion Medical Systems), similar to a pulse oximetry probe, will be placed on the patient's finger to acquire an arterial blood input function during ICG injection. After exposure but prior to debridement, 0.1 mg/kg ICG will be injected intravenously. Video rate ICG fluorescence images will be acquired 20 seconds before and 4 minutes after ICG injection. Debridement will then proceed per standard of care. The wound will be irrigated with a minimum of 3 liters irrigation with normal saline. After irrigation and debridement is completed, 0.1 mg/kg ICG will be injected intravenously again and video rate ICG fluorescence images will be acquired 20 seconds before and 4 minutes after ICG injection. There will be a minimum of 5 minutes between ICG infusions to allow ICG to wash out of tissues.

At investigator discretion, only one ICG injection may be performed and only one series of ICG fluorescence imaging will be obtained. There will be no increased risk to the subject if the investigator opts to only obtain one series of images.

5.3 Subject Compliance Monitoring

Subjects participate in a "one-time" event (i.e., surgery) as part of this study and are monitored through the in-patient surgical service during the time of their participation.

5.4 Prior and Concomitant Therapy

N/A.

5.5 Packaging

N/A

5.6 Blinding of Study Drug

N/A.

5.7 Receiving, Storage, Dispensing and Return

5.7.1 Receipt of Drug Supplies

ICG will be shipped to the Pharmacy at Dartmouth-Hitchcock Medical Center by standard UAB. Pharmacy staff will count and verify that the shipment contains all the items noted in the shipment inventory, providing temperature monitoring data to UAB if necessary. Pharmacy staff will document receipt into their electronic investigational drug management database that keeps a perpetual inventory. Any damaged or unusable study drug in a given shipment will be documented in the study files, and destroyed on site following standard procedures.

5.7.2 Storage

ICG will be stored as the original packages that shipped from the maker (Stryker).

5.7.3 Dispensing of Study Drug

Once agent assignment is performed, research staff will transport ICG in its original package to the operating room. The surgeon or anesthesiologist will prepare the solution for injection per instructions from the Stryker. 0.1mg/kg ICG will then be administered per study protocol.

5.7.4 Drug Accountability

A member of the study team will document the amount of ICG administered and any amount remaining in the institution's electronic medical record.

5.7.5 Return or Destruction of Study Drug

ICG is FDA approved for routine clinical practice. No return or destruction of study drug is needed for this study.

6 Study Procedures

Consent Process

Eligible patients regardless of ethnicity or health status, will be identified and recruited subject to inclusion and exclusion criteria above. Patients who meet eligibility criteria will be asked to participate in the trial. If they agree written informed consent will be obtained from the patient or their healthcare proxy. Patients receiving surgery in the CIS will be required to sign an additional CIS-specific surgical consent document. To obtain informed consent, study personnel (surgeon or research coordinator) will adhere to the following procedures: (1) present study information in a manner that is understandable to the patient; (2) discuss the study with the patient and answer any questions; (3) allow the patient an opportunity to discuss participation with their family; (4) confirm that the patient understands the risks and benefits of participating in the study and that their participation is voluntary; (5) complete the consent process and obtain signatures from the patient and research team. The process of obtaining and documenting informed consent forms will be completed in accordance with local Good Clinical Practice (GCP) recommendations. If the research team member obtaining consent is at all unsure about the patient's ability to consent, s/he will consult with the study PI.

Recognizing that consent is an ongoing process, the study team will encourage the participants to ask

additional questions that may arise during the course of their participation in the study.

This study will not involve the subjects who is under age 18.

The study team will comply with consent procedures outlined in SOP HRP-090.

This study does not involve the assessment of an experimental treatment to the subjects enrolled. The subjects will undergo a method for collecting imaging data that has been fully vetted and utilized in other clinical settings. The purpose of this research it to evaluate the utility of this imaging technique in orthopaedic trauma patients who have a closed orthopaedic trauma.

Cognitively Impaired Adults

Patients with impaired decision-making capacity will be included in this study. If the patient is unable to provide informed consent (e.g. due to their injury) at the time they are identified, informed consent may be obtained from their legally authorized representative (LAR). Allowing informed consent from a patient's LAR will reduce the risk of recruitment bias against the most severely infected patients.

For patient with impaired decision-making capacity, a LAR with knowledge of the potential participant will be approached to consent on the patient's behalf. If the patient cannot adequately answer at least two questions and it is determined that the patient's level of cognition is not likely to change before surgery, their LAR will be approached. The choice of LAR will follow standard procedures. The following will be approached in this order of priority:

- legal guardian
- proxy (health care agent) named in an advanced directive or durable power of attorney for health-care
- family member or other surrogate identified by state law on health care decisions.

The LAR will be advised to base the decision on the participant's expressed wishes, or, if these are not known, what they believe the participant would have desired under the circumstances of the injury, their beliefs and values. Recognizing that consent is an ongoing process, the study team will encourage the participants to ask additional questions that may arise during the course of their participation in the study.

Subjects participation in this study completely voluntary. If at any time a patient finds participation to be unduly stressful the patient or their legal authorized representative may withdraw the patient from the study with no repercussions.

Assent will not be requested from subjects unable to consent for themselves.

The study team will comply with consent procedures for cognitively impaired adults outlined in SOP HRP-013.

Surgical Procedures

In the surgery day, the patient will be prepared and transported to surgery as per routine at Dartmouth-Hitchcock. In the OR, patient positioning, preparation of the surgical field, and draping will follow standard practice, as fracture fixation or joint fusion or requiring open surgical debridement/saucerization for osteomyelitis.

A Pulse dye densometer (Pulsion Medical Systems), similar to a pulse oximetry probe, will be placed on the patient's finger to acquire an arterial blood input function during ICG injection. After exposure but prior to debridement, 0.1 mg/kg ICG will be injected intravenously. Video rate ICG fluorescence images will be acquired 20 seconds before and 4 minutes after ICG injection. Debridement will then proceed per standard of care. The wound will be irrigated with a minimum of 3 liters irrigation with normal saline. After irrigation and debridement is completed, 0.1 mg/kg ICG will be injected intravenously again and video rate ICG fluorescence images will be acquired 20 seconds before and 4 minutes after ICG injection. There will be a minimum of 5 minutes between ICG infusions to allow ICG to wash out of tissues.

A subset of 30 eligible consenting patients with post-fracture complications will undergo surgical treatment for their infection in CIS at DHMC. Patients receiving surgery in the CIS will be required to sign an additional CIS-specific consent document. For the patients who didn't receive contrast MRI in 48 hours prior to the

operation, after exposure and removal of hardware but prior to pre-debridement ICG injection, four MRI fiducials will be placed on the four corners of the damaged bone area and the MRI sequences will be acquired. Sequences will include a localizer, coronal T1 fast spin echo (FSE), axial short-tau inversion recovery (STIR), a T1 mapping sequence consisting of a T1-weighted 3D FLASH sequence with at least 3 different flip angles, and DCE acquisition, consisting of 3D FLASH sequences before and after the intravenous administration of 0.2 mL/kg Gadoterate meglumine (Dotarem®). The T1 mapping and DCE sequences will be acquired in the same plane (either the coronal or axial) for all patients. The protocol for the DCE acquisition has already been optimized for current clinical applications in the imaging of both bone and soft tissue tumors. For the patients who received MRI within 48 hours prior to the operation, we may use their pre-operation MRI, instead of intra-operative MRI.

The need for repeat debridement or tissue cultures will be left up to the treating surgeon. If repeat debridement is needed, pre- and post-debridement quantitative ICG fluorescence images will be obtained at each procedure. If the skin wound is unable to be closed, it will be left open with a sterile dressing until delayed coverage in collaboration with plastic surgery.

Upon admission and throughout the hospital course, patients will be treated with antibiotics per standard of care by the orthopaedic service or in collaboration with infectious disease recommendations. Management of study patients including clinical and radiographic assessments will not differ from standard of care.

Study participants will be followed at 6 weeks, 3 months, 6 months, 9 months and 12 months from their fracture (open and closed fracture cohorts) and from the date of consent (complication cohort), respectively. Final follow-up will be at 6 months to capture all infectious complications (Figure c.2)³⁵. If a participant does not return to clinic, follow-up may be conducted by telephone. SSI and unplanned fracture-related reoperations will be identified at the time of diagnosis/occurrence and/or during each participant clinical assessment and medical record review that will occur during their routine outpatient clinic visits.

7 Statistical Plan

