3.2 Primary Study Endpoints

The primary study endpoint for the open fracture cohort (cohort 1) is SSI using the CDC National Healthcare Safety Network reporting criteria (<https://www.cdc.gov/nhsn/pdfs/pscmanual/9pscssicurrent.pdf>) within 12 months of fracture.

The primary study endpoint for the cohort of patients with complications, (cohort 2) is treatment failure (either persistent SSI using the CDC National Healthcare Safety Network reporting criteria or persistent nonunion requiring repeat surgical procedure).

The primary study endpoint for the closed fracture cohort (cohort 3) is SSI using the CDC National Healthcare Safety Network reporting criteria.

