3.3 Secondary Study Endpoints

The secondary endpoint for all cohorts is unplanned fracture-related reoperation within 12 months of the initial open fracture. This endpoint has been used in previous fracture trials and is defined as any unplanned surgery that occurred from the time of index surgery to 12 months post-fracture that is associated with a wound healing problem, an infection at the operative site or contiguous to it, or fracture delayed union/nonunion.

4 Subject Selection and Withdrawal

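### Follow-up ends at 6 months in some sections and at 12 in others, against 12-month endpoints and power inputs, and the secondary endpoint's time origin does not fit cohorts 2 and 3

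*Combined protocol and SAP*

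**What the plan says.** Section 6 (Study Procedures, follow-up paragraph): "Study participants will be followed at 6 weeks, 3 months, 6 months, 9 months and 12 months from their fracture" for the open and closed fracture cohorts, and "from the date of consent (complication cohort") for cohort 2. The next sentence reads: "Final follow-up will be at 6 months to capture all infectious complications".

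The Study Summary sides with 6 months twice. The Methodology row has its last visit at 6 months, counted from the index study surgery, and the Duration of administration row ends participation at six months. Section 4.5.2, on withdrawn subjects, also refers to six months of clinical follow-up.

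The endpoints use a longer period or give none. In section 3.2 the cohort 1 primary endpoint is SSI "within 12 months of fracture". For cohort 2 the primary endpoint "is treatment failure (either persistent SSI using the CDC National Healthcare Safety Network reporting criteria or persistent nonunion requiring repeat surgical procedure"), with no window. For cohort 3: "The primary study endpoint for the closed fracture cohort (cohort 3) is SSI using the CDC National Healthcare Safety Network reporting criteria", again with no window in the protocol text. Section 3.3 says: "The secondary endpoint for all cohorts is unplanned fracture-related reoperation within 12 months of the initial open fracture", and then defines the period as running "from the time of index surgery to 12 months post-fracture".

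Section 7.1 bases power on 12-month event rates: 10% from fracture in cohort 1, and 30% from SSI diagnosis in cohort 2.

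**The concern.** The length of follow-up decides who counts as a case. If staff close a patient at 6 months, SSI in cohort 1 is observed for about half of its defined window, and so is reoperation. The event rates in section 7.1 then describe something other than what is measured. Contacts missed after month 6 may not be recoverable later.

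The reason section 6 gives for stopping at 6 months concerns infections only. It does not cover persistent nonunion, which is part of the cohort 2 primary endpoint. Nor does it cover reoperation for a wound healing problem or for delayed union or nonunion, which are part of the secondary endpoint.

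The time origin is a second problem. Section 3.3 applies one origin, the initial open fracture, to three cohorts. Cohort 3 has closed fractures. Cohort 2 enters after earlier definitive fixation, and sections 4.2 and 4.3 set no upper limit on time since fracture.

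**Working it through.** **Passages side by side**

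| Place | End of period | Counted from |
|---|---|---|
| Study Summary, Methodology | 6 months | index study surgery |
| Study Summary, Duration of administration | 6 months | not stated (enrolment is from consent) |
| 4.5.2 | 6 months | not stated |
| 6, visit list | 12 months | fracture (cohorts 1, 3); consent (cohort 2) |
| 6, next sentence | 6 months | not stated |
| 3.2, cohort 1 | 12 months | fracture |
| 3.2, cohorts 2 and 3 | none | none |
| 3.3, all cohorts | 12 months | initial open fracture |
| 7.1, cohort 1 | 12 months | fracture |
| 7.1, cohort 2 | 12 months | SSI diagnosis |

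Cohort 2 therefore has four time origins: index study surgery, fracture, consent and SSI diagnosis.

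**Section 3.3 window left for cohort 2.** Time left is 12 months minus time from fracture to entry. Entry at 3, 6 or 9 months leaves 12 − 3 = 9, 12 − 6 = 6 or 12 − 9 = 3 months. Entry at 12 months or later leaves none.

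**The plan's own power.** Inputs from 7.1: difference 24; SD 30 (events) and 15 (non-events); alpha 0.05; 16 vs 144 in cohort 1 and 22 vs 52 in cohort 2. Two-sided Welch test:

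SE = √(s₁²/n₁ + s₂²/n₂); noncentrality = 24/SE; Welch degrees of freedom.

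- Cohort 1: SE = √(900/16 + 225/144) = √57.81 = 7.60; noncentrality 3.16; df 15.8; power 84.1% (stated 86%).
- Cohort 2: SE = √(900/22 + 225/52) = √45.24 = 6.73; noncentrality 3.57; df 25.6; power 92.9% (stated 93%).

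The stated figures therefore rest on the full 12-month event counts.

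**Illustration if follow-up stops at 6 months.** Assumptions: total numbers are fixed, events after month 6 are counted as non-events, and early and late events share the same mean and SD. With n₂ the size of the comparison group after late events are moved into it, and m = late events / n₂, the observed difference is 24(1 − m) and the comparison-group variance is (1 − m)·225 + m·900 + m(1 − m)·24².

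Example, cohort 1 with 12 of 16 seen: n₂ = 148; m = 4/148 = 0.027; difference 23.4; SD √258.4 = 16.1; SE = √(900/12 + 258.4/148) = 8.76; noncentrality 2.67; df 11.5.

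Simulated power, two-sided Welch:

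| Events seen by month 6 | Cohort 1 | Cohort 2 |
|---|---|---|
| all (16; 22) | 84.1% | 92.9% |
| 12 of 16; 16 of 22 | 68.5% | 73.4% |
| half (8; 11) | 45.5% | 49.0% |

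The formula agrees with these within 0.2 points. A one-sided Welch test in the middle row gives about 80% and 84%.

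**The case against.** The best defence is that the weight of the text points to 12 months: the visit list, the cohort 1 endpoint, the secondary endpoint and the power inputs agree. Section 6 also says that events are identified when they occur and through record review, and section 4.4 adds telephone, text, mail and email contact. That lowers the risk. It does not remove the contradiction, because none of these routes extends a stated 6-month end, and the synopsis, which staff may well consult first, says 6 months twice.

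A second defence is that 6 months captures all infections. Section 6 asserts this with a citation and a figure that cannot be checked here. If it is true, cohort 1 loses no power for SSI. It still leaves nonunion and non-infectious reoperation uncovered.

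Four stronger readings are tempting and are not supported:

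- *The trial is underpowered.* A reader might infer this from the table above. The share of late events is not in the documents, so the table is an illustration only.
- *Power stays above 80% only if almost no events are late.* That depends on the test. Section 7.2 words its hypotheses in one direction, and one-sided Welch power is still about 80% with 4 of 16 events late. Section 7.2 also names Student's t-test. Its pooled form gives higher power still, but with these unequal SDs and group sizes it does not hold its type I error, which is a separate matter.
- *The section 3.3 time origin spoils planned analyses in cohorts 2 and 3.* Section 7.2 specifies a reoperation test for cohort 1 only (Table 7.1). Table 7.2 lists treatment failure alone, and the cohort 3 analysis compares fluorescence across cohorts.
- *Patients without contact will be counted as non-events.* The plan has no rule either way. A missing-outcome rule would be needed even if every section said 12 months, so it is a separate, optional point.

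**Conclusion.** The plan is wrong as written, and this rests on the text rather than on any calculation. Adjacent sentences of section 6 give different ends to follow-up, and the 6-month text cannot deliver the 12-month period that defines the cohort 1 primary endpoint and the secondary endpoint. If the 12-month text is followed, that loss does not arise.

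The consequence for power is conditional on stopping at 6 months and on an unknown share of late events. It ranges from no loss for SSI in cohort 1, if section 6 is right about infections, to substantial loss if a quarter or more of events come late and are counted as non-events.

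The section 3.3 time origin is a defect in the endpoint definition. It cannot be applied literally to cohort 3, and for cohort 2 the window may be partly or wholly over at entry, but it affects no test specified for those cohorts. Section 3.2 gives no window for the cohort 2 and 3 primary endpoints; the external CDC criteria it cites could not be consulted.

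**What to change.** Reconcile the Study Summary (Methodology and Duration of administration) and sections 3.2, 3.3, 4.5.2, 6 and 7.1 to one outcome window.

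- Twelve months matches the endpoints, power inputs and visit list already written. In that case, remove the 6-month statements and check that the consent form covers contact after six months.
- If 6 months is intended, redefine the cohort 1 primary endpoint and the secondary endpoint, and restate the event rates and power for that window.
- In either case, state a window for the cohort 2 and cohort 3 primary endpoints.
- Reword both phrases in section 3.3 so that cohort 3 is counted from its own fracture and cohort 2 from a single origin at or after study entry, such as consent or index study surgery. Use that origin for cohort 2 visits and endpoints alike. Note in 7.1 that the 30% rate, which runs from SSI diagnosis, is an approximation for it.

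The cost is mainly protocol wording. The 9- and 12-month contacts and telephone follow-up are already in section 6. The consent form is not visible, so a consent change for contact after six months could add cost.

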7.1 Sample Size Determination

The participating Statisticians on the study are members of the Norris Cotton Cancer Center and/or Department of Orthopaedics at Dartmouth-Hitchcock Medical Center. Sample size determination is based on the primary objective of the study as a pilot assessment of ICG fluorescence intensity of bone perfusion.

For patient cohort 1, we anticipate that approximately 10% of patients with open fracture will have an SSI within 12 months of their fracture^{1, 2, 32}. A total sample size of 160 patients will result in an estimated 16 patients with an SSI and 144 patients without an SSI. We will have 86% statistical power to detect a mean maximum fluorescence intensity (I_{max}) difference of 24 (a.u.) between the SSI group and the non-SSI group with an estimated standard deviation of 30 (a.u.) and 15 (a.u.), respectively. All parameters were obtained from our previous porcine study. To be conservative, we increased the standard deviation by 50% for this power calculation. The type I error is set to be 5%. If we assume a drop-out rate of 10%, then a total of 176 patients will be enrolled.

For patient cohort 2, we anticipate approximately 30% of patients with an SSI will go on to develop a persistent SSI/treatment failure within 12 months of diagnosis of their SSI¹². Based on this estimate, a sample size of 22 patients with SSIs and 52 patients without, will have 93% statistical power to detect a mean I_{max} difference of 24 (a. u.) between the persistent SSI/treatment failure group and the non-persistent SSI/non-treatment failure group with I_{max} estimated standard deviation of 30 (a. u.) and 15(a. u.). All parameters are obtained from our previous porcine study, which are consistent with a pilot study conducted at STC in human participants using ICG fluorescence for a different indication. To be conservative, we increased the standard deviation by 50% for this study. The type I error is set to be 5%. If we assume the dropout rate is 10%, then a total of 82 patients will be recruited.

For patient cohort 2-1, the strength of the relationship between DCE-MR and DCE-FI measurements will

be assessed by determining the zero-order correlation and resulting R2 metric. A sample of 21 was estimated utilizing formula presented by Bonett & Wright ³⁶ with a Type I error rate of 0.05 and Type II error

rate of 0.20 (1-Power) to estimate the magnitude of zero-order correlation and interval estimation. Formula inputs included expected zero-order relationship of $r = 0.85$ (95% CI 0.55 to 1.00). To optimize the imaging parameters of DCE-MRI, extra seven patients has been added into this cohort. Thus, total of 30 patients will be involved in this cohort.

Patient cohort 3 will serve as the control group for cohorts 1 and 2.

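### Section 7.1: multiplying by 1.1 leaves slightly fewer evaluable patients than planned, and cohort 1's 86% power is a fixed-count figure that becomes about 81% once the SSI count varies (two-sided Welch test)

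*Combined protocol and SAP*

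**What the plan says.** All the sizing is in Section 7.1. For cohort 1 the event rate is an approximation: "we anticipate that approximately 10% of patients with open fracture will have an SSI within 12 months of their fracture". The split follows from it: "A total sample size of 160 patients will result in an estimated 16 patients with an SSI and 144 patients without an SSI". At that split the plan states: "We will have 86% statistical power to detect a mean maximum fluorescence intensity". The target is a "difference of 24 (a.u.) between the SSI group and the non-SSI group", "with an estimated standard deviation of 30 (a.u.) and 15 (a.u.), respectively", at a 5% type I error. It adds: "To be conservative, we increased the standard deviation by 50% for this power calculation". Enrolment is then set: "If we assume a drop-out rate of 10%, then a total of 176 patients will be enrolled".

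Cohort 2 uses the same difference and SDs with 22 treatment failures and 52 non-failures, 74 in all, for a stated 93%. It ends: "If we assume the dropout rate is 10%, then a total of 82 patients will be recruited".

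Section 7.1 names neither the power formula nor the sidedness, and it gives no power at any other number of events. Section 7.2 plans Student's t-tests and states a directional hypothesis, with lower post-debridement intensity in the group with the bad outcome.

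**The concern.** There are two separate issues.

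First, an allowance for dropout rate d should divide the evaluable target by (1 − d). Multiplying by (1 + d) falls short, so the enrolment figures do not deliver the evaluable numbers that the power statements use.

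Second, patients enter cohort 1 before their outcome is known, so the number of SSIs is random. Almost all the variance of the comparison comes from the small SSI group, and power is concave in the SSI count: a shortfall costs more than an equal excess gains. Power at the expected count is therefore higher than power averaged over the counts that could occur.

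What is at stake is how a null result in cohort 1 would be read. With 11 or 12 SSIs it would be set against a claimed 86%, although the power at those counts is much lower and the plan does not show it.

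**Working it through.** **Inputs (Section 7.1).** Difference 24; SD 30 (event group) and 15 (non-event group); 5% type I error; SSI rate 10% in cohort 1 and failure rate 30% in cohort 2; dropout 10%; evaluable 160 (16 + 144) and 74 (22 + 52); enrolled 176 and 82. The 50% SD increase is read as already contained in 30 and 15. Applying it again gives 50.7% in cohort 1 and 62.9% in cohort 2, far from the stated powers.

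**Step 1: reproduce the stated powers.** For the unequal-variance (Welch) t-test, SE = √(30²/n₁ + 15²/n₂), the noncentrality is 24/SE, the degrees of freedom are Satterthwaite's, and power comes from the noncentral t distribution.

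- Cohort 1: SE = √(900/16 + 225/144) = √(56.25 + 1.56) = 7.60; noncentrality 24/7.60 = 3.16; df 15.8; two-sided 5% power **84.1%** (simulation 84.2%).
- Cohort 2: SE = √(900/22 + 225/52) = 6.73; noncentrality 3.57; df 25.6; power **92.9%**.

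| Method | Cohort 1 (stated 86%) | Cohort 2 (stated 93%) |
|---|---|---|
| Welch, two-sided 5% | 84.1% | 92.9% |
| Normal approximation, unequal SDs, two-sided 5% | 88.4% | 94.6% |
| Welch, one-sided 5% | 91.5% | 96.6% |
| Pooled t, common SD 30, two-sided 5% | 85.5% | 87.4% |

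Two-sided Welch fits the pair best. It matches cohort 2 and comes within 2 points for cohort 1.

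**Step 2: dropout.**

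- Cohort 1: 160 × 1.1 = 176, and 176 × 0.9 = 158.4 completers. Dividing instead, 160/0.9 = 177.8, so 178.
- Cohort 2: 74 × 1.1 = 81.4, rounded up to 82, and 82 × 0.9 = 73.8 completers. Dividing instead, 74/0.9 = 82.2, so 83.

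**Step 3: let the event count vary.** Averaged power = Σₖ P(K = k) × power(k, N − k), with K binomial.

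| Cohort 1, two-sided Welch | Power |
|---|---|
| Fixed 16/144 | 84.1% |
| Averaged over Binomial(160, 0.10) | 81.6% |
| Averaged over Binomial(158, 0.10) | 81.1% |

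Cohort 2 averages 91.9% with 74 patients and 91.6% with 73.

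**Step 4: split the cohort 1 gap.** From 86% to 84.1% is 1.9 points, the difference between the stated figure and the Welch value. From 84.1% to 81.6% is 2.5 points, from the varying count. From 81.6% to 81.1% is 0.5 point, from the dropout inflation. The last two total about 3 points.

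**Step 5: spread.** Cohort 1 power by SSI count is 61% at 10, 71% at 12, 78% at 14, 84% at 16 and 92% at 20. The chance of 12 or fewer SSIs is 17.9% with 160 patients and 19.3% with 158.

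**The case against.** The strongest reply has four parts.

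- **Expected counts are ordinary practice.** The plan says approximately 10% and calls the 16 an estimate, within a study that Section 7.1 describes as a pilot assessment. This stands. Using 16/144 is not an arithmetic error, and averaging over the count is a refinement.
- **The dropout shortfall is tiny.** It is two patients in cohort 1 and one in cohort 2. Section 4.5.2 keeps withdrawn patients who complete clinical follow-up in the imaging and infection analysis, and Sections 4.4 and 6 allow remote follow-up, so actual loss may be below 10%. With no loss, 176 patients give 85.5% averaged power. This stands as to size, but 176 and 82 still do not yield 160 and 74 at the plan's own dropout rate.
- **The 81% depends on a test the plan does not name.** With 158 completers, the averaged power is 86.0% under the two-sided normal approximation and 89.1% under a one-sided 5% Welch test. This stands as a condition on the result. Those methods fit the two stated powers less well, and the normal approximation ignores the t penalty when the high-variance group has about 16 patients. A pooled Student's t does not help: with these SDs and group sizes its two-sided type I error is about 25%, so its apparent 97% power means little.
- **Uncertainty in the rate matters more.** With 158 completers, averaged power is 71% at a true SSI rate of 8% and 88% at 12%. This stands, and it supports showing a range.

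A reader might infer that the fixed count and the dropout factor together explain the whole fall from 86% to 81%. They do not: about 2 of those 5 points are already there at exactly 16/144.

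**Conclusion.** The point holds as a minor one. At 10% dropout the stated enrolment leaves about 158 and 73 to 74 evaluable patients rather than 160 and 74; this needs no modelling assumption. Under the best-fitting test, cohort 1 power is 84.1% at the expected count and 81.1% averaged over the SSI count at 158 completers. The loss due to the varying count and the dropout arithmetic is about 3 points, almost all of it from the count. Cohort 2 falls by about 1 point.

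The power figures rest on a two-sided 5% Welch test, SDs of 30 and 15 as final values, a binomial count and a true SSI rate of exactly 10%. A reader might conclude that cohort 1 is underpowered. The documents do not support that: averaged power stays above 80% on these inputs. What the plan leaves out is the roughly one-in-five chance of 12 or fewer SSIs, where power is 71% or less.

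**What to change.** In Section 7.1:

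- Name the test and the sidedness used for power, and make them agree with the test and directional hypothesis in Section 7.2.
- State that 176 and 82 enrolled give about 158 and 73 evaluable patients after 10% dropout. If 160 and 74 are wanted, the matching enrolments are 178 and 83. For cohort 1 that raises averaged power only to 81.6%, so restating is enough.
- Restate cohort 1 power as about 84% at the expected count and about 81% averaged over the SSI count, and cohort 2 as about 92%, on the assumptions of a two-sided Welch test and true event rates of 10% and 30%. If a different test is named, recompute these figures.
- Show cohort 1 power at 12 SSIs (71%) and 20 SSIs (92%), and note a chance of about 18–19% of 12 or fewer.

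The cost is a few sentences and slightly less favourable stated figures. Enrolment and study procedures need not change.
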